8.3 Per Protocol Set

The Per Protocol Set (PPS) will consist of all FAS subjects, excluding those for whom major protocol deviations have been identified. This population will be used for supportive analysis of the response rate and other efficacy parameters.

Since the study is closing early, the PPS is no longer applicable.

8.4 Pharmacokinetic Population

All subjects who receive at least one full or partial dose of either study treatment (i.e. are included in the Safety Population) with at least one analyzable blood sample will be included in the pharmacokinetic population.

9. General Statistical Considerations

9.1 Unit of Analysis

The unit of analysis in this study will be the subject for all efficacy and safety summaries.

9.2 Missing Data and Adjustments for Multiplicity

This is a phase 2, exploratory study. Missing values will not be estimated. All data will be included in safety analysis. Censoring rules for time to event analyses are described in Section 14. Since no

statistical testing will be performed, there will be no adjustments for multiplicity. Fleming's procedure is based on a one sample hypothesis test for a proportion. Because there is a single primary hypothesis, treatment corrections for multiplicity are not required.

9.3 Definition of Baseline

Baseline is defined as the last measurement prior to the first dose of study medication. In Treatment Period 1 this will be the last measurement prior to the first dispensing of MA (Visit -3). In Treatment Period 2 this will be the last measurement prior to the first in-clinic administration of MA and SC (Visit 1, Day 0-TP2). For subjects treated in both Treatment Period 1 and Treatment Period 2, baseline resets at the start of Treatment Period 2. Change from baseline will be calculated as the value at the time point of interest minus the baseline value.

9.4 Data Analysis Conventions

All data analysis will be performed by SDC after the study is completed and the database has been locked. Statistical programming and analyses will be performed using SAS® Version 9.4 or higher. Output will be provided in portable document format (PDF) and Excel. All study data will be listed by subject and visit (as applicable) based on all enrolled subjects unless otherwise specified.

Summaries for continuous and ordinal variables will include the number of observations (n), arithmetic mean, standard deviation, median, minimum, and maximum). Minima and maxima will be reported with the same precision as the raw values; means and medians will be presented to one additional decimal place than reported in the raw values. Standard deviations will be presented to two additional decimal places than reported in the raw values. Summaries for discrete variables will include frequency counts and percentages. All percentages will be rounded to one decimal place (i.e., XX.X%). The baseline measure will be defined as the last non-missing measure prior to initiation of investigational treatment.

9.5 Visit Windows

Each Study Visit has an acceptable window for when it must occur (Protocol Section 5.4). Any visit that falls outside of the acceptable window must be clearly documented as a protocol deviation.

9.6 Analysis Conventions

Disposition, safety and PK data will be reported for: Subjects in Treatment Period 1 only, Subjects in Treatment Period 2 only, Subjects in Treatment Period 1 Followed by Treatment Period 2, All Treatment Period 1 Subjects, All Treatment Period 2 Subjects, and All Subjects. Efficacy data will be reported for: Subjects in Treatment Period 2 only, Subjects in Treatment Period 1 Followed by Treatment Period 2, All Treatment Period 2 Subjects, and All Subjects.

10. Disposition of Subjects

10.1 Disposition and Discontinuation

Subject disposition including which subjects were enrolled in, completed or discontinued from each Treatment Period participated in Follow-Up and, if applicable, time in Follow-Up will be presented in a listing. Screen failure subjects will be also presented in a listing, including the reasons for screen failure.

The possible reasons for screen failure are:

- Eligibility Criteria Not Met
- Physician Decision
- Withdrawal of Consent
- Adverse Event
- Other

The reasons for discontinuation from Treatment Period 1 (prior to Week 12) are:

- Disease Progression
- AE
- Withdrawal of Consent
- Pregnancy
- Non-Compliance
- Death
- Lost to Follow-Up
- Concurrent Illness
- Physician's Decision
- Protocol Deviations
- Sponsor Termination of Study
- Other

Some Treatment Period 1 subjects will proceed to Treatment Period 2 and others will not proceed.

Reasons for not proceeding to Treatment Period 2 are:

- Disease Control (CR, PR, or SD)

- AE
- Withdrawal of consent
- Pregnancy
- Non-Compliance
- Death
- Lost to Follow-Up
- Concurrent Illness
- Physician's Decision
- Protocol Deviations
- Sponsor Termination of Subject
- Subject Did Not Receive at Least 4 Weeks of Treatment in Treatment Period 1
- Other

The reasons for Sodium Cridanimod treatment discontinuation (in Treatment Period 2) are:

- Disease Progression
- AE
- Withdrawal of consent
- Pregnancy
- Non-Compliance
- Death
- Lost to Follow-Up
- Concurrent illness
- Other

The reasons for not completing Safety Follow-Up are:

- AE
- Lost to Follow-Up

- Physician's Decision
- Protocol Deviations
- Sponsor Termination of Study
- Withdrawal of Consent
- Other

A subject listing of informed consent date(s) and applicable protocol amendment versions will also be provided.

10.2 Analysis Populations

A subject listing of analysis populations and treatment periods will be provided including reasons for exclusion.

10.3 Visit Dates

A subject listing of all visit dates for each will be presented.

10.4 Protocol Deviations

Protocol deviations will be collected and monitored by the site monitors and transferred to SDC as an Excel spreadsheet. Protocol deviations are collected for the following categories:

- Assessment Not Done
- Assessment Out of Window
- Inclusion/Exclusion Criteria
- Safety Related
- Visit Not Done

Prior to database lock, deviations will be reviewed to determine major/minor status. Any violations of the inclusion or exclusion criteria or subject compliance in study drug administration outside of the 80-120% acceptable range will be considered major protocol deviations. A subject listing will be provided including the date of the deviation, the deviation category and description and the classification of whether the deviation was judged to be major or minor.

11. Demographic and Pretreatment Variables

11.1 Demographic Variables

The following demographic and baseline characteristics of subjects will be provided in a listing.

- Age

- Sex
- Race
- Ethnicity
- Screening GOG Performance Status
- Screening Height
- Screening Weight

Age will be reported in years and calculated using the following formula:

$$\text{Age} = \text{floor} ((\text{informed consent date} - \text{date of birth}) + 1) / 365.25$$

11.2 Pretreatment Variables

Listings of subjects receiving prior cancer therapies (chemotherapies, hormonal therapies, radiation therapy and surgery) will be provided. Number of cycles, and best response will be presented for prior chemotherapies. Listings of these data will also include indication (as text field for prior chemotherapies) and indication plus localization (as text fields for prior radiotherapies)

11.3 Cancer Disease History and PrR Status

Subject cancer history including histology (serous adenocarcinoma or endometrioid carcinoma), date of histology assessment, TNM stage, and PrR status, intensity, percent of nuclei staining, date of tumor sample and date of central lab results will be presented in a listing.

11.4 Medical History

Listings of medical history data using the Medical Dictionary for Regulatory Activities (MedDRA®) dictionary, version 20.0, by System Organ Class (SOC) and Preferred Term (PT) will be generated, including the applied coding terms.

11.5 Pregnancy Testing

Pregnancy tests are applicable to all subjects of childbearing potential (i.e. excluding those who are anatomically sterile or are post-menopausal). A serum pregnancy test (measuring *-human chorionic gonadotropin [β -hCG]) will be performed at the Screening Visit, and a urine pregnancy test will be performed at the End of Study-TP1 Visit, at Visit 7, Visit 13, and the Safety Follow-Up TP2 Visit. Results of pregnancy testing will be reported in a subject listing.

12 Concomitant Medications

Concomitant medication is defined as any medication, other than the investigational medicinal product (SC) and MA, taken at any point in the duration from the Screening Visit until the End of Study-TP1 Visit

or the Safety Follow-Up TP2 Visit. This includes all prescription medications, over-the-counter medications, and herbal remedies. All concomitant medications will be recorded. A subject listing of concomitant medications will be provided. Medications administered prior to first dose of study drugs will be distinguished from those administered once study drug dosing has begun.

13. Dosing Compliance and Treatment Exposure

13.1 Dosing Compliance

Treatment compliance will be monitored by the review of study drug accountability, inventory records by study personnel, and subject diaries. Treatment compliance (for each study drug individually) lower than 80% or higher than 120% will be considered a major protocol deviation. In the case of poor compliance, the reason for the discrepancy will be documented in the eCRF and the Investigator, together with the Sponsor, will decide on a clinical basis as to whether the subject may remain in the study. For SC, all doses are administered at the clinic or by qualified personnel at the subject's home and are recorded on the Study Drug Administration eCRF. For MA, at all visits following the Screening Visit, the subject will be provided with a Patient Diary and asked to record the administration of their daily doses of megestrol acetate (including those taken in clinic during a study visit). In addition, subjects are to record any AEs and concomitant medications in the diary. Diaries will be completed by the subjects until they exit the study at the End of Study-TP1 Visit or the Safety Follow-up TP2 Visit. Subjects will be instructed to return their completed diary at each Study Visit and a new diary will be provided to the subject.

13.2 Treatment Exposure

Subject listings of all exposure/dosing variables will be provided, including dosing days and times, lot number for SC, dose delays for SC and number of tablets per dose and other diary data for MA. Additionally, a listing of MC accountability data will be provided, including number of dispensed and returned tablets and bottles, number of tablets taken since previous visit and lot number will be produced.

14. Efficacy Analyses

The efficacy variables include the following:

- ODCR
- ORR
- Duration of SD
- PFS
- OS

Note that since the study is closing early, no summaries of overall disease control rate, or overall response rate will be calculated as part of the final analysis. However, best overall response, duration of SD (where applicable), PFS and OS for each subject in Treatment Period 2 will be listed.

Tumor response will be determined in accordance with RECIST 1.1 criteria using objective measurements of target lesions, assessments of non-target lesions and identification of new lesions. Disease response utilizes the categories: CR, PR, SD, Progressive Disease (PD), and Not Evaluable (NE).

A disease or tumor assessment will be performed by clinical examination for palpable or visual tumor lesions as well as by CT or MRI. Tumor assessments will be performed at Screening, during Treatment Period 1 following 12 weeks of treatment (at Visit -1) of Treatment Period 1, and, if disease control is achieved at that time, after an additional 12 weeks of treatment (at Visit TP1-EXT), and continuing during Treatment Period 2 every 12 weeks (\pm 7 day window) until disease progression is documented. CT scan or MRI of chest, abdomen, and pelvis are appropriate, but all scans for an individual subject must use the same procedure as was performed at baseline. Conventional CT and MRI should be performed with contiguous cuts of 10mm or less in slice thickness. Spiral CT should be performed by use of a 5 mm contiguous reconstruction algorithm. Ultrasound should not be used for measurement. Clinically detected lesions will only be considered measurable if they are superficial (e.g. skin nodules and palpable lymph nodes). For skin lesions, documentation by color photography, including a tool to estimate size of the lesion, is recommended.

For evaluating subject responses during Treatment Period 2, the tumor assessments for determining progression in Treatment Period 1 will be used as the new baseline measurements. For subjects entering Treatment Period 2 directly, the tumor assessments from Screening will be used as the baseline measurements. From this point forward any objective responses (CR, PR) must be confirmed at least 4 weeks after the criteria for response are first met. Once subjects progress during Treatment Period 2, they will return for a Safety Follow-Up TP2 Visit four (4) weeks following the last treatment, and then continue to be followed for an additional 12-month period for survival. If a subject discontinues Treatment Period 2 for any reason other than disease progression (i.e. intolerable AE), every reasonable effort should be taken to encourage subjects to continue receiving regular tumor assessments until disease progression is documented, with the date of disease progression still recorded in the eCRF.

If at any point during either Treatment Period, the Investigator feels that the subject's clinical status warrants radiographic assessment an unscheduled scan may be performed. If disease progression is observed at an unscheduled scan during TP1, the subject is eligible to enter TP2 if she has received $>$ 4 weeks of treatment, otherwise the subject must return for an End of Study-TP1 Visit and be discontinued from the trial. If disease progression is observed at an unscheduled scan during TP2, the

subject must be withdrawn from treatment, enter the Follow-up Period and return for the Safety Follow-up TP2 Visit. An Unscheduled scan eCRF is to be completed.

Subjects with a global deterioration of health status requiring discontinuation of treatment in Treatment Period 2 without objective evidence of disease progression at that time should be classified as having symptomatic deterioration. Reasonable efforts should be taken to obtain radiographic evidence to confirm disease progression. Subjects experiencing symptomatic deterioration during Treatment Period 1 without objective evidence of disease progression are ineligible to enter Treatment Period 2 (as they do not meet the inclusion criteria requiring radiographic evidence of progression).

A listing of target lesions will present lesion site, description, measurement (in mm), type (nodal vs extranodal), whether the lesion is visible or palpable, was the lesion area previously irradiated, number of lesions assessed, method of assessment, CT/MRI slice thickness and whether contrast median was used. A second listing will summarize target lesion sums of diameters, percentage change from baseline, the investigator-determined overall time point target lesion assessment, sites of new lesions and method of evaluation of new lesions. This listing will also include percentage change from nadir, and which visits were used for baseline and nadir measurements for treatment period 2. Additionally, a listing of non-target lesions sites, description, status, investigator-determined overall time point non-target lesion assessment and number of non-target lesions assessed will be provided (including which visits were used for baseline assessments for subjects participating in Treatment Period 2).

14.1 Determination of Response

At each disease assessment time point Investigators assign a disease response category based on RECIST 1.1. Inclusion criteria for this trial include the presence of measurable disease with at least one target lesion to use for all disease assessments. All measurable lesions up to a maximum of 2 lesions per organ and 5 lesions in total, representative of all involved organs, should be identified as target lesions and recorded and measured at baseline. All other lesions (or sites of disease) including any measurable lesions over and above the 5 target lesions should be identified as non-target lesions and should also be recorded at baseline. Measurements of these lesions are not required, but the presence or absence of each should be noted throughout the study. If a subject misses a disease assessment, or the Investigator declines to assign a response category at an assessment, response for this assessment will be designated NE.

The following table summarizes the determination of overall disease assessment for a given time point.

Evaluation of Time Point Response: Subjects with target (+/- non-target) disease*

Target Lesions	Non Target Lesions	New Lesions	Overall Response	Confirmation Scan (Treatment Period 2 only)
CR	CR	No	CR	Yes
CR	Non CR/Non PD	No	PR	Yes
CR	Not Evaluated	No	PR	Yes
PR	Non CR/Non PD/Not Evaluated	No	PR	Yes
SD	Non CR/Non PD	No	SD	No
PD	Any	Yes or No	PD	No
Any	PD	Yes or No	PD	No
Any	Any	Yes	PD	No

*Derived from *New Response Evaluation Criteria in Solid Tumours: Revised RECIST guideline (version 1.1)*,
Table 1

14.2 Minimum Criteria for Stable Disease Determination

For SD to be assigned, the criteria for SD must be met at least once after a minimum of 6 weeks following first dose of study drug (in Treatment Period 1 following first dose of MA, in Treatment Period 2 following the first doses of SC and MA).

14.3 Determination of Best Overall Response

At the conclusion of study drug treatment in Treatment Period 2, the best overall response for each subject who participates in Treatment Period 2 will be determined. Best overall response is defined as the best overall RECIST response recorded from the start of the Treatment Period 2 until the end of this treatment period, ordering response categories from best to worst: CR, PR, SD, PD, and NE. The subject's best response assignment will depend on the achievement of both measurement and confirmation criteria. If a timepoint response of 'NE' follows a response of "CR" or "PR," the next evaluable timepoint response will be used for confirmation.

A swimmer's plot which includes the duration of exposure for each Treatment Period, response over time, duration of follow-up, and best overall response for each subject in the Safety population who participates in Treatment Period 2 will be presented.

Best overall response when confirmation of CR and PR required*

Overall Response First Time Point	Overall Response Subsequent Time Point	Best Overall Response
CR	CR	CR
CR	PR	SD, PD or PR ^a

CR	SD	SD provided minimum criteria for SD duration met, otherwise, PD ^a
CR	PD	SD provided minimum criteria for SD duration met, otherwise, PD ^a

^aIf a CR is truly met at first time point, then any disease seen at a subsequent time point, even disease meeting PR criteria relative to baseline, makes the disease PD at that point (since disease must have reappeared after CR). Best response would depend on whether minimum duration for SD was met. However, sometimes 'CR' may be claimed when subsequent scans suggest small lesions were likely still present and in fact the patient had PR, not CR at the first time point. Under these circumstances, the original CR should be changed to PR and the best response is PR.

*Derived from *New Response Evaluation Criteria in Solid Tumours: Revised RECIST guideline (version 1.1)*, Table 3

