5.6.3. Evaluations of a Subject's Best Overall Response

The best overall response is the best response recorded from the start of Treatment Period 2 until disease progression/recurrence (taking as reference for progressive disease the smallest measurements recorded since the treatment started). The subject's best response assignment will depend on the achievement of both measurement and confirmation criteria.

Table 13. Best overall response when confirmation of CR and PR required*

Overall Response First Time Point	Overall Response Subsequent Time Point	Best Overall Response
CR	CR	CR
CR	PR	SD, PD or PR
CR	SD	SD provided minimum criteria for SD duration met, otherwise, PD
CR	PD	SD provided minimum criteria for SD duration met, otherwise, PD
CR	NE	SD provided minimum criteria for SD duration met, otherwise, NE
PR	CR	PR
PR	PR	PR
PR	SD	SD
PR	PD	SD provided minimum criteria for SD duration met, otherwise, PD
PR	NE	SD provided minimum criteria for SD duration met, otherwise, NE

*Derived from *New Response Evaluation Criteria in Solid Tumours: Revised RECIST guideline (version 1.1)*, Table 5

First Documentation of Response: The time between the initiation of Treatment Period 2 and the first documentation of PR or CR.

Confirmation of Response: To be assigned a status of CR or PR, tumor measurements must be confirmed by repeat assessment performed at least four weeks after the criteria for response are first met.

Duration of Response: The period of time from the disease assessment at which measurement criteria are first met for CR or PR (whichever status is recorded first) until the first date that recurrent or progressive disease is objectively documented.

Duration of Complete Response (CR): The period of time from the disease assessment at which criteria for CR are met until the first date that recurrent disease is objectively documented.

Duration of Stable Disease: The time from the initiation of combination therapy on Study Visit 1 in Treatment Period 2 until the criteria for disease progression are first met.

Disease Control: Disease control is defined as all Best Overall Responses that are not progressive disease (i.e. SD, PR or CR).

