4.4.4. Special notes on response assessment

When nodal disease is included in the sum of target lesions and the nodes decrease to 'normal' size (<10 mm), they may still have a measurement reported on scans. This measurement should be recorded even though the nodes are normal in order not to overstate progression should it be based on increase in size of the nodes. As noted earlier, this means that patients with CR may not have a total sum of 'zero' on the case report form (CRF).

In trials where confirmation of response is required, repeated 'NE' time point assessments may complicate best response determination. The analysis plan for the trial must address how missing data/assessments will be addressed in determination of response and progression. For example, in most trials it is reasonable to consider a patient with time point responses of PR-NE-PR as a confirmed response.

Patients with a global deterioration of health status requiring discontinuation of treatment without objective evidence of disease progression at that time should be reported as 'symptomatic deterioration'. Every effort should be made to document objective progression even after discontinuation of treatment. Symptomatic deterioration is not a descriptor of an objective response: it is a reason for stopping study therapy. The objective response status of such patients is to be determined by evaluation of target and non-target disease as shown in Tables 1–3.

Conditions that define 'early progression, early death and inevalability' are study specific and should be clearly described in each protocol (depending on treatment duration, treatment periodicity).

In some circumstances it may be difficult to distinguish residual disease from normal tissue. When the evaluation of complete response depends upon this determination, it is recommended that the residual lesion be investigated (fine

Table 3 – Best overall response when confirmation of CR and PR required.

Overall response First time point	Overall response Subsequent time point	BEST overall response
CR	CR	CR
CR	PR	SD, PD or PR ^a
CR	SD	SD provided minimum criteria for SD duration met, otherwise, PD
CR	PD	SD provided minimum criteria for SD duration met, otherwise, PD
CR	NE	SD provided minimum criteria for SD duration met, otherwise NE
PR	CR	PR
PR	PR	PR
PR	SD	SD
PR	PD	SD provided minimum criteria for SD duration met, otherwise, PD
PR	NE	SD provided minimum criteria for SD duration met, otherwise NE
NE	NE	NE

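### SAP 14.3 attaches RECIST footnote a to the CR-then-SD and CR-then-PD rows, where its last sentence contradicts the table cells and the SAP's own confirmation rule

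*SAP*

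**What the plan says.** SAP 14.3 gives a table for deriving best overall response when CR and PR need confirmation, and cites RECIST 1.1 Table 3 as its source. The rows for CR followed by SD and CR followed by PD carry the footnote marker: "SD provided minimum criteria for SD duration met, otherwise, PD ^a".

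Footnote a has two parts:

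- If the first CR was genuine, any disease seen later is progression, and "Best response would depend on whether minimum duration for SD was met".
- If later scans suggest that "in fact the patient had PR, not CR at the first time point", then "Under these circumstances, the original CR should be changed to PR and the best response is PR".

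The second part does not mention a second scan at PR level.

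Three statements require confirmation:

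- SAP 14.3: "The subject's best response assignment will depend on the achievement of both measurement and confirmation criteria".
- SAP section 14, text before 14.1, for Treatment Period 2: "any objective responses (CR, PR) must be confirmed at least 4 weeks after the criteria for response are first met".
- Protocol 5.6.3: "To be assigned a status of CR or PR, tumor measurements must be confirmed by repeat assessment performed at least four weeks after" the response criteria are first met.

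In the appended RECIST Table 3, the CR-then-SD and CR-then-PD rows read "SD provided minimum criteria for SD duration met, otherwise, PD" with no marker. Protocol Table 13 has the same rows and no footnote a.

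**The concern.** In RECIST the footnote is safe because of the row it sits on. When CR is followed by PR and the first scan is re-read as PR, the sequence becomes PR-PR, which is a confirmed PR. On the two rows added in the SAP, the same re-reading gives PR-SD or PR-PD. Neither is a confirmed response, yet the footnote's last sentence still names PR as the best response.

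A programmer therefore has two instructions for one sequence: the cell gives SD or PD, and the footnote gives PR. Best overall response is one of the few derived efficacy results that the abbreviated analysis keeps. It appears in Listing 16.2.6.4 and in the swimmer's plot (Figure 14.2.1.1). It also decides who enters Listing 16.2.6.5, because SAP 14.6 defines duration of SD only for subjects whose best response is SD. With 25 women enrolled (SAP 4.5) and results read subject by subject, one ambiguous label would be noticed.

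**Working it through.** This is a classification rule and the plan states no figure to reproduce, so the check sets the tables side by side.

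**Step 1: where the footnote sits, and what each source gives.** The last column relabels the first CR as PR and reads the result from Protocol Table 13. RECIST Table 3 has the same PR rows.

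| Sequence | SAP 14.3 cell | Footnote a in RECIST Table 3 | Footnote a in SAP 14.3 | Footnote's last sentence, read literally | Relabel CR as PR, then Protocol Table 13 |
|---|---|---|---|---|---|
| CR, PR | SD, PD or PR | yes | yes | PR | PR-PR = PR |
| CR, SD | SD if minimum met, else PD | no | yes | PR | PR-SD = SD |
| CR, PD | SD if minimum met, else PD | no | yes | PR | PR-PD = SD if minimum met, else PD |

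On the first row the footnote, the cell and Table 13 are compatible. On the other two, the footnote's last sentence gives an outcome that neither the cell nor Table 13 contains.

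**Step 2: is the conflict settled elsewhere?** SAP section 1 says that the SAP's methods replace the protocol's, so Table 13 does not automatically prevail. SAP section 20 describes changes from the protocol and does not mention this one, so nothing shows that it was intended. The SAP's own confirmation statements point to SD or PD, but the footnote is the most specific text on a re-read CR.

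**Step 3: would disease control change?** SAP 14.2 sets the SD minimum at 6 weeks after first dose: 6 × 7 = 42 days. The first scheduled Period 2 scan is at week 12, with a 7-day window (Protocol 5.5.2): 12 × 7 − 7 = 77 days at the earliest. Since 77 > 42, the minimum is met. This counts a CR scan as at least SD, as the CR-then-PD row needs if it is ever to give SD. The choice is then PR against SD, and both count as disease control. A change from PD to PR would need an unscheduled first scan before day 42.

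**Step 4: which outputs depend on it?** ODCR and ORR are not calculated (SAP 3.1, 14.4, 14.5). What remains is Listing 16.2.6.4, the swimmer's plot and Listing 16.2.6.5. A subject labelled PR instead of SD would drop out of the last of these.

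**The case against.** The strongest reply is that the SAP does not authorise an unconfirmed PR. The cells on both rows exclude PR, while the CR-then-PR cell lists it. The table's title, SAP 14.3 and the text of SAP section 14 all require confirmation. These are SAP provisions, so the clause by which the SAP replaces protocol methods does not remove them. This stands. A reader might infer from the marker alone that the SAP credits responses that failed confirmation; the documents support only an internal contradiction.

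The marker also has a sensible explanation. The first part of the footnote fits both rows: disease after a genuine CR is progression, and the minimum SD duration then decides between SD and PD. That may be why the marker was added. It explains the placement but leaves the last sentence attached to rows it does not fit.

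A reader might also want to express the problem as points of ORR. No such result will exist, because neither rate is calculated and SAP 3.5 plans no hypothesis test. Lesion data by visit are also listed (Listings 16.2.6.1 to 16.2.6.3), and the swimmer's plot shows response over time, so a mislabelled sequence could be spotted.

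Finally, the SAP table as read shows no rows starting with PR. That may be a loss in reading the PDF, and it is not counted as an error here.

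**Conclusion.** The point holds as an internal contradiction in a derivation rule. On the CR-then-SD and CR-then-PD rows, the last sentence of footnote a disagrees with the cells it annotates, with the SAP's confirmation requirement, and with Protocol Table 13 once the first scan is relabelled. Two programmers could code the same subject differently.

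The practical size is small. It needs a first CR that is later judged to have been a PR and is then followed by SD or PD. CR is assumed to be rare here; the documents give no expected CR rate for the combination. At scheduled scans, disease control is unaffected on the step 3 reading of the SD minimum. What can change is an individual subject's entry in the best overall response listing and the swimmer's plot, and whether she appears in the duration-of-SD listing. It is still worth correcting, because those listings carry much of the efficacy reporting that remains.

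**What to change.** Either of two edits to SAP 14.3 is enough:

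- Keep footnote a on the CR-then-PR row only, as in RECIST Table 3.
- Or keep the marker where it is and add that a CR re-read as PR still needs confirmation and is rescored from the PR rows of Protocol Table 13: PR-PR = PR; PR-SD = SD; PR-PD = SD if the minimum SD duration is met, otherwise PD.

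Referring to Table 13 works whether or not the SAP table prints its own PR-first rows. The cost is a table or footnote edit before the listings are programmed, with no new data or analyses. If such a sequence has occurred, the subject would be listed as SD or PD under the stated rule.
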